2.8.2 Laboratory values

Laboratory values will be converted to SI units and analyzed using NCI CTCAE grades version 4.03 or later.

For laboratory tests where grades are not defined by CTCAE, results will be graded by the low/normal/high classifications based on laboratory normal ranges.

The following by-visit summaries will be generated separately for hematology:

- shift tables using CTCAE grades to compare baseline to the worst on-treatment value,
- for laboratory tests where CTCAE grades are not defined, shift tables using the low/normal/high/(low and high) classification to compare baseline to the worst on treatment value
- Listing of all laboratory data with values flagged to show the corresponding CTCAE grades and the classifications relative to the laboratory normal ranges.

Boxplots will be presented for selected hematology over time using Safety set.

Listing for serum and urine pregnancy data will also be provided by patients where available using Safety set.

2.8.3 ECG analysis

Not applicable

2.8.4 Analysis of vital signs

Vital sign assessments will be performed in order to characterize basic body function. The parameters collected are weight (kg), body temperature (°C), sitting systolic and diastolic blood pressure (mmHg).

Clinically notable elevated values are defined as:

- Systolic BP: 160 mmHg and an increase 20 mmHg from baseline
- Diastolic BP: 100 mmHg and an increase 15 mmHg from baseline
- Body temperature: 39.1°C
- Weight: increase from baseline of 10%

Clinically notable below normal values are defined as:

- Systolic BP: 90 mmHg and a decrease 20 mmHg from baseline
- Diastolic BP: 50 mmHg and a decrease 15 mmHg from baseline
- Body temperature: 35°C
- Weight: decrease from baseline of 10%

Vital signs shift table based on values classified as notable low, normal, notable high or notable (high and low) at baseline and worst post-baseline will be produced for weight, body temperature and sitting diastolic and systolic BP using Safety set.

Vital signs data (weight, body temperature, pulse rate, sitting systolic blood pressure and diastolic blood pressure) will be summarized by visit and Safety set will be used.

Descriptive statistics will be tabulated for baseline and change from baseline at each post-baseline time point for each vital sign measure using Safety set.

Patients with clinically notable vital sign abnormalities will be listed using Safety set. All vital sign assessments will be listed by patient and vital sign parameter. In the listings, clinically notable values will be flagged.

2.9 CSR Section 9.7.2 – Sample size and power considerations

2.9.1 Sample size

The planned sample size of approximately 500 patients was chosen based on the expected accrual rates and the planned duration of the trial. It was not based on any statistical consideration. The actual sample size may differ from this planned number.

2.9.2 Power for analysis of key secondary variables

Not applicable

3 Appendix 16.1.7 Randomization scheme and codes

This section of the RAP document presents a short account of the randomization procedures.

**Clinical
Development**

INC424

INC424B2401

**Appendix 16.1.7: Randomization scheme and
codes**

Document type: Clinical Study Report - Appendix 16.1.7

Property of
Novartis
Confidential

May not be used, divulged, published or otherwise
disclosed without the consent of Novartis

3.1 Randomization scheme and codes

Each patient is identified in the study by a Patient Number that is assigned when the patient is first enrolled for screening and is retained as the primary identifier for the patient throughout his/her entire participation in the trial. The Patient No. consists of the Center Number (Center No., as assigned by Novartis to the investigative site) with a sequential patient number suffixed to it, so that each patient is numbered uniquely across the entire database. Upon signing the informed consent form, the patient is assigned to the next sequential Patient No.

Since this is an open label single arm study, **no** randomization will be needed; however, IRT (Interactive Response Technology) will be used to assign patient numbering. The investigator or designated staff will contact the IRT and provide the requested identifying information for the patient to register them into the IRT. Once assigned, the Patient Number must not be reused for any other patient and the Patient Number for that individual must not be changed, even if the patient is re-screened. If the patient fails to be dosed, the reason will be entered into the Screening Log page.

3.2 Treatment assignment

Prior to dosing, all patients who fulfill all entry criteria will be assigned to treatment via IRT. The investigator or his/her delegate will contact the IRT and confirm that the patient fulfills the protocol's entry criteria.

3.3 Treatment blinding

Not applicable

**Clinical
Development**

INC424

INC424B2401

4.1.1 Study day

Definitions will be applied for all situations:

- Study day for post-randomization event = event date – first dose date + 1
- Study day for pre-randomization event = randomization date - event date

The first day of study drug is study day 1.

If duration is to be reported in weeks, duration in days will be divided by 7, likewise if in months, then duration in days will be divided by 30.4375 and if in years, duration in days will be divided by 365.25.

4.2 Analysis populations

The populations are detailed in Section 9.7.1 of the Clinical Study Report.

4.3 Safety evaluations

The text below gives more detailed instructions and rules needed for programming of the analyses described in [Section 2.8.1](#).

4.3.1 Baseline

The last available assessment before or on the start date of study drug is defined as “baseline” value or “baseline” assessment. If an assessment is planned to be performed prior to the first dose of study drug in the protocol and the assessment is performed on the same day as the first administration of study drug, it will be assumed that it was performed prior to study drug administration, if assessment time point is not collected or is missing. If assessment time points are collected, the observed time point will be used to determine pre-dose on study day 1 for baseline calculation. Unscheduled assessments will be used in the determination of baseline.

Patients who will start treatment and discontinue from the study on the same day may have 2 different sets of data collected on study day 1, one being reported to day 1 visit, the other reported to the end of treatment (EOT) visit. Data reported at the EOT visit are not eligible for baseline selection.

4.3.2 Multiple assessments within post-baseline visits

For all analyses regarding abnormal assessments or analyses based on worst post-baseline value (vital signs, ECOG performance status), all post-baseline values will be included (scheduled, unscheduled, repeat). All unscheduled and repeat measurements will be included in listings.

4.4 Handling of missing or partial dates

For patients not known to have died prior to the cut-off date:

- All events with start date before or on the cut-off date, and with end date missing or after the cut-off date will be reported as “continuing at the cut-off date”.
- This approach applies, in particular, to AEs and concomitant medication reports. For these events, the end date will not be imputed and therefore will not appear in the listings.

For patients known to have died prior to or on the cut-off date:

- All events with start date before or on the cut-off date, and with end date missing or after the cut-off date will have the end date imputed to the death date.
- This approach applies, in particular, to AEs and concomitant medication reports. For these events, the imputed end date will not appear in the listings.

Partial AE start date	Treatment start date	Relationship	Imputation calculation	Imputed date
12mmYYYY	20OCT2001	Uncertain	NC	<blank>
ddmmm2000	20OCT2001	Before	(D)	01JUL2000
ddmmm2002	20OCT2001	After	(E)	01JAN2002
ddmmm2001	20OCT2001	Uncertain	(B)	21OCT2001
ddSEP2001	20OCT2001	Before	(C)	15SEP2001
ddOCT2001	20OCT2001	Uncertain	(B)	21OCT2001
ddNOV2001	20OCT2001	After	(A)	01NOV2001

4.4.2 Incomplete date of initial diagnosis of cancer and date of most recent recurrence

Missing day is defaulted to the 15th of the month and missing month and day is defaulted to 01-Jan.

4.4.3 Incomplete date for anti-neoplastic therapies

Prior therapies

Start date:

The same rule which is applied to the imputation of AE/concomitant medication start date will be used with the exception that for scenario (B) will be replaced to be 'start date of study drug -1'.

End date:

Imputed date = min (start date of study drug, last day of the month), if day is missing; Imputed date = min (start date of study drug, 31DEC), if month and day are missing.

If the end date is not missing and the imputed start date is after the end date, use the end date as the imputed start date.

If both the start date and the end date are imputed and if the imputed start date is after the imputed end date, use the imputed end date as the imputation for the start date.

Post therapies

Start date

Imputed date = max (last date of study drug + 1, first day of the month), if day is missing;

Imputed date = max (last date of study drug + 1, 01JAN), if day and month are missing.

4.4.4 Incomplete date for death

All dates must be completed with day, month and year.

If the day or month is missing, death will be imputed to the maximum of the last contact date (excluding the date of death) and the following:

- Missing day: 15th of the month and year of death
- Missing day and month: July 1st of the year of death

4.4.5 Incomplete dates for last dose of INC424

Scenario 1

If the last date of study drug is after the cut-off date or is completely missing and there is no end of treatment eCRF page and no death date the patient should be considered to be on-going and use the cutoff date for the analysis as the last dosing date

Scenario 2

If the last date of study drug is completely or partially missing and there is EITHER an end of treatment eCRF page OR a death date available then imputed last dose date:

- = 31DECYYYY, if only Year is available and Year < Year of min (EOT visit date, death date)
- = Last day of the month, if both Year and Month are available and Year = Year of min (EOT visit date, death date) and Month < the month of min (EOT visit date, death date)
- = min (EOT visit date, death date), for all other cases

The imputed date will be compared with start date of study drug.

If the imputed date < start date of study drug, then last date of study drug is set to start date of study drug; otherwise, use the imputed date.

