6.1.5 Treatment duration

Patients may continue ruxolitinib treatment until they experience any of the following:

- Disease progression determined by the local investigator (see [Appendix 4](#) and [Appendix 5](#)),
- Unacceptable toxicity that precludes further treatment,
- Start of a new anti-cancer therapy,
- Pregnancy,
- Treatment is discontinued at the discretion of the investigator or patient,
- Lost to follow-up or withdrawn consent,
- Death,
- Study terminated by the sponsor,
- Study is completed (see definition below).

Treatment duration is considered “completed” three months after ruxolitinib becomes commercially available in the patients participating country or by 31 December 2017, whichever comes first, and the patient should be transitioned to commercial product. Study sites should stop all patients’ study participation on the ETP at this time.

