7.1.3 End of treatment visit including study completion and premature withdrawal

At the time patients discontinue study treatments, a visit should be scheduled as soon as possible, at which time all of the assessments listed for the End of Treatment (EOT) visit will

be performed and an End of treatment CRF page will be completed giving the date and reason for stopping treatment.

At a minimum, all patients who discontinue treatment, including those who refuse to return for a final visit, will be contacted for safety evaluations 30 days following the last dose of treatment by phone.

Patients who discontinue treatment should be considered withdrawn after the final visit assessments are performed or when it is clear that the patient will not return for these assessments.

If a withdrawal occurs, or if the patient fails to return for visits, the investigator must determine the primary reason for a patient's premature withdrawal from the study and record this information on the study Evaluation Completion CRF page.

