2.1 CSR Section 9.7.1 Statistical and analytical plans

The statistical analysis of these data will be performed by Novartis personnel in accordance with the data analysis section, Section 10, of the study protocol which is available in [Appendix 16.1.1 of the CSR](#). Important information is given in the following sections and details are provided, as applicable, in [Appendix 16.1.9 of the CSR](#). SAS version 9.4 will be used in all analyses.

This is a global, single arm, open-label, multi-center trial designed to provide early access and evaluate the safety of ruxolitinib in patients with polycythemia vera who are HU resistant or intolerant and who have no other standard treatment options. Efficacy and patient reported outcomes will also be assessed.

Final analyses will be performed when all patients have been followed for 30 days after they have either prematurely discontinued or been discontinued from the study after completing treatment as per protocol (i.e., until the drug is commercially available for this indication in each participating country).

It is planned that the data from all centers that participate in this trial will be pooled and analyzed. Unless otherwise specified, qualitative data will be described using frequency and percentages, while quantitative data, will be described using descriptive statistics: n, mean, standard deviation, median, minimum, and maximum.

No interim analysis is planned, and the final analysis will be performed after all patients have either completed the study or have been prematurely discontinued from the study.

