2.4 Patients and treatments

2.4.1 Patient disposition

Patient disposition will be summarized using the Full analysis set (FAS). The following will be tabulated:

- Number (%) of patients screened;
- Number (%) of patients enrolled;
- Number (%) of patients, who remained in the trial at the time of data cut-off;
- Number (%) of patients who discontinued the treatment;
- Number (%) of patients with primary reason for end of treatment (based on patient status entered in the 'END OF TREATMENT DISPOSITION' page);
- Number (%) of patients with primary reason for end of study (based on completion of 'STUDY EVALUATION COMPLETION' page);

Listings will be provided for disposition, inclusion/exclusion criteria and the screening logs.

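### SAP 4.4.5 Scenario 1 credits dosing up to the cut-off date when the last-dose date, EOT page and death date are all missing, although nobody can still be on treatment at the final analysis

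*SAP*

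**What the plan says.** SAP 4.4.5 has two scenarios for an incomplete last-dose date.

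- **Scenario 1.** If the last date of study drug "is completely missing and there is no end of treatment eCRF page and no death date the patient should be considered to be on-going", the instruction is to "use the cutoff date for the analysis as the last dosing date".
- **Scenario 2.** If the date is completely or partially missing and "there is EITHER an end of treatment eCRF page OR a death date available then imputed last dose date" is derived from the earlier of the EOT visit date and the death date, or from the end of a recorded earlier month or year. The cut-off date plays no part.

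On timing, SAP 2.1 plans no interim analysis and states that "the final analysis will be performed after all patients have either completed the study or have been prematurely discontinued from the study".

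On the pages available, protocol 7.1.3 asks for an EOT visit when treatment stops, at which "an End of treatment CRF page will be completed giving the date and reason for stopping treatment". Protocol 6.1.5 counts "Lost to follow-up or withdrawn consent" among the events that end treatment. For a withdrawal, or a patient who fails to return for visits, protocol 7.1.3 tells the investigator to establish the primary reason and "record this information on the study Evaluation Completion CRF page". Protocol 7.1.3.1 says only that loss to follow-up goes on the eCRF, without naming a page. SAP 2.4.1 tabulates the end-of-study reason "based on completion of 'STUDY EVALUATION COMPLETION' page", so the second page is in the analysis database.

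**The concern.** Scenario 1 takes the absence of an EOT page and a death date as evidence that the patient is still taking ruxolitinib. That is reasonable at a data cut taken while treatment continues. It cannot be right in an analysis that waits until everyone has completed or discontinued, where a missing last-dose date is a gap in the record.

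The rule does not look at the Study Evaluation Completion page, the last visit, the last dosing record or the last contact date, although SAP 4.4.4 already uses last contact for incomplete death dates. A patient who stops attending may have the page that the rule ignores and lack the one it needs.

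Safety is the primary objective, and the last-dose date feeds much of its reporting:

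- duration of exposure and dose intensity (SAP 2.4.6.1);
- the end of the on-treatment period, 30 days after last dose (SAP 2.8);
- the patient-years behind the exposure-adjusted SAE and safety-event-category summaries (SAP 2.8.1).

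A lost patient contributes few or no observed events after leaving. The added time is therefore close to event-free and pulls the adjusted rates down.

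**Working it through.** The plan states no figure on this point, so there is none to reproduce. The check applies the rule as written and then sizes it on stated assumptions.

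**1. Which patients reach which rule (final analysis, last-dose date not fully recorded)**

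| Last-dose date | EOT page or death date? | Rule | Last dose set to |
|---|---|---|---|
| Completely missing | Yes | Scenario 2 | Earlier of EOT visit and death |
| Completely missing | No | Scenario 1 | Cut-off date |
| Partially missing | Yes | Scenario 2 | End of recorded month or year, or earlier of EOT visit and death |
| Partially missing | No | None | Undefined |

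Row 2 is the wrong rule. Row 4 is a gap: Scenario 1 requires a completely missing date (or one after the cut-off), and Scenario 2 requires an EOT page or a death date.

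**2. One patient**

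Formulas from SAP 2.4.6.1: duration = last date − first date + 1; DI = cumulative dose / duration; RDI = 100 × DI / PDI.

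Assumptions: true last dose on day 168 (Week 24); 20 mg/day throughout; cut-off 31 December 2017. The SAP gives no calendar cut-off; this is the latest country end date in protocol 4.3. Three first-dose dates are tried.

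| First dose | True days | Scenario 1 days | Ratio | Extra years | DI if cumulative dose stays at 168 × 20 = 3,360 mg |
|---|---|---|---|---|---|
| 1 Dec 2014 | 168 | 1,127 | 6.7 | 959/365.25 = 2.63 | 3,360/1,127 = 3.0 mg/day |
| 1 Dec 2015 | 168 | 762 | 4.5 | 594/365.25 = 1.63 | 3,360/762 = 4.4 mg/day |
| 1 Dec 2016 | 168 | 396 | 2.4 | 228/365.25 = 0.62 | 3,360/396 = 8.5 mg/day |

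The true DI is 20 mg/day. Duration cancels in RDI, so its distortion depends on programming. If planned dose runs to the cut-off while actual dose does not, RDI falls to 15%, 22% or 42%. If the open dosing record is carried forward for both, RDI is unchanged but cumulative dose is overstated (1,127 × 20 = 22,540 mg in the first row).

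For comparison, if the same patient had an EOT page dated 28 days after the last dose, Scenario 2 would give 168 + 28 = 196 days.

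**3. Whole study**

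Inflation of patient-years = share affected × extra years / mean true exposure. Assumptions: mean true exposure 1 year; extra time 0.5 to 2 years per affected patient; true rate 20 SAEs per 100 patient-years; no events in the added time. Reported rate = 20 / (1 + inflation).

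| Share affected | Inflation | Reported rate per 100 patient-years |
|---|---|---|
| 1% | 0.5% to 2% | 19.9 to 19.6 |
| 2% | 1% to 4% | 19.8 to 19.2 |
| 5% | 2.5% to 10% | 19.5 to 18.2 |

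The percentages do not depend on the number of patients. They halve if mean true exposure is 2 years.

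**4. Could the patient have been dosing to the cut-off?**

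Protocol 6.6 (Table 6-5) supplies tablets until the next scheduled visit, and protocol 4.1 sets visits 4 weeks apart to Week 24 and 12 weeks apart after that. A patient last seen at Week 24 holds about 84 days of drug. Scenario 1 adds 228 to 959 days.

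**The case against.** The best defence is that the rule rarely applies. Protocol 7.1.3 calls for an EOT page when treatment stops, and protocol 6.1.5 treats loss to follow-up as ending treatment. A reader might infer that every patient lost to follow-up is credited with exposure to the end of the study. The documents do not support that: a lost patient with an EOT page goes to Scenario 2. Nor does protocol 7.1.3 say that the Study Evaluation Completion page replaces the EOT page. In addition, last dose is taken from the dosing record (SAP 2.4.5) and missing values are queried before lock (protocol 9.4), so several failures must coincide.

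Much of this stands, and it limits the number affected. It does not make the rule right for those who remain. Their existence is plausible, because protocol 7.1.3 ties the EOT page to a visit and names the other page for patients who do not return.

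A second defence is that a wrong status need not mean a badly wrong date. A patient treated until shortly before the cut-off, with an EOT page never filed, gets nearly the right date. That is also fair. The large errors belong to patients lost early. Extreme cases can be built: first dose 1 October 2015 and loss after 28 days gives 823 days against 28, about 29-fold. Such a case says little about the study total.

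Third, the number-and-percentage adverse event tables do not use patient-years, and no hypothesis is tested. This is true, but those tables still depend on the on-treatment window, and the exposure-adjusted summaries are planned outputs.

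Finally, protocol 10.7 allows unplanned analyses for regulators or publication, when patients could really be on drug. That is a reason to restrict Scenario 1 rather than delete it.

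**Conclusion.** The point holds in a limited form. In the only planned analysis, Scenario 1 gives the wrong treatment status to any patient with a completely missing last-dose date, no EOT page and no death date, and it can greatly overstate exposure for one lost early. Separately, and without any assumption, a partially missing date with no EOT page and no death date has no rule.

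The effect is large for a single patient (2.4- to 6.7-fold in the cases shown) and small to moderate for pooled rates: about 0.5% to 10% of patient-years if 1% to 5% of patients are affected. Those shares, the mean exposure, the extra time and the cut-off date are all assumptions, since the documents do not say how many patients are affected. The expected direction is towards lower exposure-adjusted rates, which flatters safety. The rule should be corrected because it is wrong as stated and the remedy uses data already collected.

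**What to change.** Rewrite SAP 4.4.5 as follows.

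1. **On-going rule.** Use the cut-off date as last dosing date only in an unplanned analysis done while patients are still on treatment (protocol 10.7), and then only if there is no EOT page, no death date and no Study Evaluation Completion page. State that no patient is classed as on-going in the final analysis.
2. **Final analysis.** For every patient with a completely or partially missing last-dose date and no EOT page or death date, whether or not a Study Evaluation Completion page exists, impute the last date on which dosing is documented: the Dosage Administration Record, otherwise the last contact date. Keep the result within any recorded month or year and no later than the last contact date or the cut-off. This also closes the partial-date gap.
3. **Transparency.** List the imputed cases, so that the number and the added time can be seen.

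The cost is a few lines of SAP text and programming, with no new data. The downside is a slight undercount for patients who went on taking dispensed tablets after the last documented date. Given the visit spacing, that is about 4 weeks per patient up to Week 24 and about 12 weeks (84/365.25 = 0.23 years) later, against 0.62 to 2.63 years of overcount in the cases above.

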2.4.6.1 Dose intensity and exposure

Definitions of duration of exposure, cumulative dose, average daily dose, actual dose intensity (DI), planned dose intensity (PDI), relative dose intensity (RDI), percentage of days dosed, percentage of days the planned/intended dose was received, as well as intermediate calculations, include:

- Duration of exposure (days): last date of study drug – first date of study drug + 1
- Cumulative dose (mg): total dose of study drug taken by a patient in the study
- Number of dosing days (days): duration of exposure – number of zero dose days
- % Days dosed: $100 \times \text{number of dosing days} / \text{duration of exposure (days)}$
- % Days with planned dose: $100 \times \text{number of days with planned dose} / \text{duration of exposure (days)}$
- Average daily dose (mg/day): cumulative dose (mg) / number of dosing days (days)
- DI (mg/day): cumulative dose (mg) / duration of exposure (days)
- PDI (mg/day): cumulative planned dose (mg) / duration of exposure (day)
- RDI (%): $100 \times \text{DI (mg/day)} / \text{PDI (mg/day)}$

Duration of exposure to study drug, actual cumulative dose, percentage of actual days dosed, percentage of days the planned dose was received, average daily dose, DI and RDI (including categories: <70, 70-90, >90) will be summarized descriptively. In addition, the duration of exposure to study drug will be categorized into time intervals; frequency counts and percentages of patients with exposure in each time interval will be presented.

The derived parameters above will also be listed using Safety set.

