2.8 Safety evaluation

The overall observation period will be divided into mutually exclusive segments:

We have

1. pre-treatment period: from day of patient's informed consent to the day before first dose of study medication
2. on-treatment period: from day of first dose of study medication to 30 days after last dose of study medication
3. If applicable, post-treatment period: starting at day 31 after last dose of study medication.

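### The last-dose imputation in SAP 4.4.5 has no branch for a known month in an earlier calendar year, so it returns an impossibly late date and lengthens exposure and the on-treatment window

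*SAP*

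**What the plan says.** SAP 4.4.5, Scenario 2, opens: "If the last date of study drug is completely or partially missing and there is EITHER an end of treatment eCRF page OR a death" – that is, whenever an EOT page or a recorded date of death exists. Call the earlier of the EOT visit date and the death date the reference date. Three branches follow.

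- **Year only, earlier year:** "31DECYYYY, if only Year is available and Year < Year of min (EOT visit date, death date").
- **Year and month, same year:** "Last day of the month, if both Year and Month are available and Year = Year of min (EOT visit date, death date"), and the recorded month is before the reference month.
- **Everything else:** "min (EOT visit date, death date), for all other cases".

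One check comes afterwards, a lower bound: "If the imputed date < start date of study drug, then last date of study drug is set to start date". No check compares the imputed date with the year and month that were recorded.

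The result is used widely. SAP 2.4.6.1 defines duration of exposure as "last date of study drug – first date of study drug + 1". SAP 2.8 sets the "on-treatment period: from day of first dose of study medication to 30 days after last dose of study medication". SAP 2.8.1 builds treatment-emergent AEs, on-treatment deaths and the exposure-adjusted SAE and safety-event-category summaries on these quantities. The concomitant-medication window (2.4.7) and the start-date imputation for post-study antineoplastic therapy (4.4.3) also depend on the last dose date.

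**The concern.** A last dose with known month and year, in a year before the reference year, fails the first branch because more than the year is known. It fails the second because the years differ. It drops to the catch-all and takes the reference date, which lies in a later year than the recorded one and so cannot be right.

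This does not look like a chosen convention. The first branch respects an earlier recorded year and the second respects an earlier recorded month; only their combination is missing. As a result, a less complete record gets a possible date and a more complete one gets an impossible date.

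Safety is the primary objective, and the error goes in one direction only. Exposure and patient-years are overstated, and events after the true on-treatment window can be counted inside it. Protocol 6.1.5 ends treatment three months after commercial availability "or by 31 December 2017, whichever comes first, and the patient should be transitioned to commercial product". A December last dose with a January EOT visit is therefore a plausible way to cross a year boundary.

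**Working it through.** The plan states no figure for this rule, so there is none to reproduce. The check applies the three branches literally.

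**Inputs.** Branches and lower bound: SAP 4.4.5. Duration = last dose − first dose + 1: SAP 2.4.6.1. Window end = last dose + 30 days: SAP 2.8. The dates below, including a first dose on 15JAN2016, are illustrative assumptions.

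**Excess = imputed date − last day of the recorded month.**

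| Recorded last dose | Reference date | SAP result | Latest possible date | Excess (days) |
|---|---|---|---|---|
| 2016 (year only) | EOT 10JAN2017 | 31DEC2016 | 31DEC2016 | 0 |
| NOV2016 | EOT 20DEC2016 | 30NOV2016 | 30NOV2016 | 0 |
| DEC2016 | EOT 10JAN2017 | 10JAN2017 | 31DEC2016 | 10 |
| DEC2017 | EOT 10JAN2018 | 10JAN2018 | 31DEC2017 | 10 |
| DEC2016 | EOT 27JAN2017 | 27JAN2017 | 31DEC2016 | 27 |
| NOV2016 | EOT 10JAN2017 | 10JAN2017 | 30NOV2016 | 31 + 10 = 41 |
| NOV2016 | EOT 20JAN2017 | 20JAN2017 | 30NOV2016 | 31 + 20 = 51 |
| OCT2016 | EOT 15FEB2017 | 15FEB2017 | 31OCT2016 | 30 + 31 + 31 + 15 = 107 |

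The first two rows are controls that the rule handles correctly. In the DEC2017 row the imputed last dose falls after the protocol's own final treatment date.

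**Effect on derived quantities** (first dose 15JAN2016, last dose NOV2016, EOT 10JAN2017):

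- As written: duration 362 days, window to 09FEB2017.
- With month end: duration 321 days, window to 30DEC2016.
- Difference: 362 − 321 = 41 days in both.

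**A death.** Last dose NOV2016, no EOT visit date, death on 15FEB2017. The rule sets the last dose to the death date, so the death is on-treatment by construction. The latest possible dose was 30NOV2016, which is 31 + 31 + 15 = 77 days before death and outside the 30-day window.

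**All patterns.** The rule was run for every reference date from 01JAN2016 to 31DEC2017 and every true last dose 0 to 365 days earlier, with the day missing or with day and month missing. For a known month in an earlier year, the imputed date contradicted the record in 133,590 of 133,590 combinations. Every other pattern gave 0 contradictions. With the second branch extended to earlier years, all patterns gave 0. These counts show where the logic fails, not how often such records occur.

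**The case against.** The gap itself is hard to dispute. The case against concerns its reach and importance.

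- **Rarity.** Three things must coincide: day missing, month and year present, and EOT or death in a later calendar year. Doses go on the Dosage Administration Record (Protocol 6.1.1), the EOT page asks for the stopping date (7.1.3), and missing values are queried before lock (9.4). This stands, and the number is probably small. But the rule exists for the dates that queries leave unresolved.
- **Long gaps are illustrative.** Protocol 7.1.3 wants the EOT visit soon after stopping, so the 51-day and 107-day cases need a late visit or a late death. This stands. However, no maximum gap is set, and the same section foresees patients who decline a final visit.
- **Year-end timing.** 31 December 2017 is a latest date, many countries could finish earlier, and Protocol 4.3 ends the study by then, so a January 2018 visit is off schedule. This limits frequency. Such a visit remains plausible after a December stop.
- **Dose intensity.** Relative dose intensity is a ratio of two quantities with the same duration in the denominator, so duration cancels. Actual dose intensity does use duration, but how far it moves depends on whether cumulative dose is also extended over the imputed days, which the SAP does not say. This qualification stands.
- **Few late events.** AE monitoring is required for at least 30 days after last dose (8.1.1), and later SAEs are reported only if suspected to be related (8.2.2). The widened window may therefore capture few extra events. Death classification and patient-years are still affected.
- **Pooled effect.** Assume 5 of 500 patients are shifted by 30 days each: mean exposure moves by 5 × 30 / 500 = 0.3 days. For 1 to 20 patients the range is 0.06 to 1.2 days. No hypothesis is tested.

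**Conclusion.** The concern holds. As written, SAP 4.4.5 gives an impossible last-dose date whenever month and year are known and the year precedes that of the EOT visit or death. The date is always too late, and no later step corrects it. Duration of exposure, patient-years and the 30-day on-treatment window lengthen by the same number of days: 10 to 107 in the tabulated cross-year examples, depending on the assumed dates.

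The size in this trial cannot be stated, because the documents give neither the number of partial last-dose dates nor the distribution of the gap to the EOT visit. Pooled exposure would hardly change under the assumptions above. The practical risk lies with individual patients: in a single-arm safety report that lists deaths and SAEs, one event can be classed as on-treatment through imputation alone. That warrants correction, given how little it costs.

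**What to change.** Extend the condition of the second branch in SAP 4.4.5, Scenario 2. When year and month are both recorded, impute the last day of that month if either:

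- the recorded year is before the year of the reference date; or
- the years are equal and the recorded month is before the reference month.

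Keep the first branch, the catch-all and the lower bound at first dose unchanged.

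The cost is one condition in the SAP and in the derivation program. No new data are needed, and every case the present rule handles correctly keeps its date. It would also help to report how many last-dose dates were imputed through this branch.
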